4.1. DATA MONITORING COMMITTEE (DMC)

There will be no planned DMC for this study.

4.2. INTERIM ANALYSIS

No interim analysis is planned for this study.

4.3. FINAL ANALYSIS

All final, planned analyses identified in this SAP will be performed by IQVIA Biostatistics following Sunovion authorization of this SAP, Sunovion authorization of analysis population, database lock, and unblinding of treatment.

All PK/PD analysis will be described in a separate analysis plan.

5. ANALYSIS POPULATIONS

Agreement and authorization of subjects included/ excluded from each analysis set will be conducted prior to the unblinding of the study.

5.1. SCREENED [SCR] SUBJECTS

The screened subjects (SCR) set contains of all subjects who provided informed consent for this study.

5.2. ENROLLED [ENR] POPULATION

The enrolled (ENR) population contains all screened subjects who passed screening, defined as all of the eligibility criteria met at screening visit.

Document:

\

Author:

Version Number:
Version Date:Final 1.0
24FEB2020Template No: CS_TP_BS016 Revision 4
Effective Date: 01Apr2016

Reference: CS_WI_BS005

5.3. RANDOMIZED [RND] POPULATION

The all subjects randomized (RND) population contains all subjects in the ENR set who had given their informed consent and were randomized to study medication.

For analyses and displays based on RND, subjects will be classified according to randomized treatment.

5.4. MODIFIED INTENT-TO-TREAT [mITT] POPULATION

The modified intention-to-treat (mITT) population is defined as all subjects who were randomized, received at least one dose of study drug, and had a baseline and at least one post-baseline total score in SAPS-PD or NPI or CGI-S during the DB treatment period.

The mITT population will be the primary population for the efficacy analyses. Subjects will be analyzed according to randomized treatment group.

5.5. mITT COMPLETE CASES [mITTComp1] SAPS-PD POPULATION

The mITT complete cases (mITTComp) is defined as all subjects of the mITT who completed SAPS-PD assessment at the Week 6 visit (Visit 7 not including the ET visit), and have Baseline and Week 6 SAPS-PD total score data available. If a subject had missing SAPS-PD data at visits other than Week 6 (i.e. Visits 3 [Week 1], Visit 4 [Week 2], Visit 5 [Week 3], or Visit 6 [Week 5]), or if he had missing data in assessments other than SAPS-PD at Week 6 (Visit 7), this subject will still be included in the complete case analysis for SAPS-PD total score. Week 6 visit is defined in the protocol as study visit day 43 (+/-2 days). The mITT Complete cases population will be reviewed in a similar manner as the Per-Protocol population as some subjects may have performed a Week 6 visit outside of the visit window but they are still completers.

5.6. mITT COMPLETE CASES [mITTComp2] CGI-S POPULATION

Same as mITTComp1, for CGI-S instead.

The mITTComp1 and mITTComp2 populations will be used for the complete case analysis of the SAPS-PD total score and CGI-S score respectively. Subjects will be analyzed according to randomized treatment group.

Document:

\

Author:

Version Number:
Version Date:Final 1.0
24FEB2020Template No: CS_TP_BS016 Revision 4
Effective Date: 01Apr2016

Reference: CS_WI_BS005

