3.4. DETERMINATION OF SAMPLE SIZE

A total of approximately 36 subjects will be randomized in 2:1 ratio to SEP-363856 and placebo, with approximately 24 subjects assigned to SEP-363856 and 12 subjects assigned to placebo. The sample size will provide powers of 59%, 48%, 37%, and 27% to detect treatment effect sizes of 0.8, 0.7, 0.6, and 0.5, respectively, in change from Baseline in SAPS-PD at Week 6 for SEP-363856 versus placebo. It was estimated by using a two independent sample t-test method with 2-sided significant level of 0.05. The sample size was determined for the purposes of exploring the efficacy, safety and tolerability of flexible dosing with SEP-363856 (25, 50, or 75 mg/day) for 6 weeks in male and female subjects with a clinical diagnosis of PDP. A sufficient number of subjects will be enrolled to ensure 36 randomized subjects.

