15.1.4.2. Pattern-mixture model with placebo-based multiple imputation

The MMRM model used in the primary analysis makes the assumption that data are missing at random (MAR). However, the missing data mechanism may or may not be at random. Sensitivity to the missing data assumptions will be tested by using the pattern-mixture model with placebo-based multiple imputation method (Ratitch, O'Kelly, & Tosiello, 2013), exploring the robustness of the MMRM results of the primary efficacy analysis. In this analysis, missing values in the SEP-363856 (25, 50 or 75 mg/day) treatment group will be imputed based on data of the placebo group, assuming that, after withdrawal, subjects from the SEP-363856 (25, 50 or 75 mg/day) group will exhibit the same future evolution of Parkinson's as subjects from the placebo group, and that subjects who discontinue from the placebo group will exhibit the same future evolution of Parkinson's as subjects in the placebo group remaining in the study. This approach does not assume a sustained benefit of experimental treatment after discontinuation.

Two separate imputation procedures are used to impute missing values. Firstly, the Markov chain Monte Carlo (MCMC) method is used to perform partial imputation to obtain datasets with monotone missing patterns. Then a sequential regression multiple imputation method is used to impute the monotone missing values.

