The remaining monotone missing data will be imputed using sequential regression multiple imputation, where a separate regression model is estimated for imputation of each variable (i.e., SAPS-PD total score at each time point). Imputation of values in the placebo group will assume MAR. Imputation of values in the SEP-363856 (25, 50 or 75 mg/day) group will be done as if the subject had been a member of the placebo group. Missing values in the SEP-363856 (25, 50 or 75 mg/day) group will be imputed using the imputation model of the placebo group, i.e., conditional on subject values observed at time points prior to discontinuation relative to the mean of the model for the placebo group. Each sequential regression model (i.e., for imputation of values at a given time point) will include explanatory variables for all previous (Baseline, Week 1, 2, 3 and 5) values of SAPS-PD total score. Missing values at a given time point in placebo and SEP-363856 (25, 50 or 75 mg/day) arms will be imputed from the same imputation model, conditional on subject values observed or imputed at previous time points. The SAS MI procedure with the MONOTONE REG statement is used to specify that the regression method will be used for the imputation, and the MNAR statement with MODEL option will be used for the SAPS-PD total score at each post-baseline visit to specify that only observations from the placebo group should be used to estimate the imputation model. The random seed number is 12345.

No rounding restriction will be applied to imputed SAPS-PD total scores. The imputed SAPS-PD total scores must be within the range of 0 to 45.

Document:

\

Author:

Version Number:

Final 1.0

Version Date:

24FEB2020

Template No: CS_TP_BS016 Revision 4
Effective Date: 01Apr2016

Reference: CS_WI_BS005

Each of the 1000 imputed datasets will be analyzed using the same MMRM model as the primary efficacy analysis. Results from the analysis of each imputed dataset, i.e. the LS means of each treatment group, the LS mean treatment difference, and their standard errors, will be combined using Rubin's imputation rules (using the SAS MIANALYZE procedure) to produce pooled LS mean estimates, their standard errors and 95% CI, and a pooled p-value for the test of null hypothesis of no treatment effect.

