15.1.4.3. Tipping point analysis

Sensitivity to departures from the MAR assumption will also be investigated using a tipping point analysis. In this analysis, departures from MAR in the SEP-363856 (25, 50 or 75 mg/day) group will be assessed assuming that subjects who discontinue the study have, on average, efficacy outcomes after discontinuation that are worse by some amount δ compared to other similar subjects with observed data at the same time point (i.e., compared to a value which would have been assumed under a MAR model).

A series of analyses will be performed with increasing values of δ until the analysis conclusion of a statistically significant treatment effect no longer holds. The value of δ that overturns the primary results will represent a tipping point. An interpretation of clinical plausibility of the assumption underlying the tipping point will be provided.

Change from baseline in SAPS-PD total score will be analyzed based on data observed while the subject remains on study as well as data imputed using multiple imputation methodology for the time points at which no value is observed. Intermittent (non-monotone) missing data will be imputed first based on the MAR assumption and a multivariate joint Gaussian imputation model using the MCMC method within each treatment arm, as described above for the pattern-mixture model with placebo-based multiple imputation.

The remaining monotone missing data will be imputed using sequential regression multiple imputation, where a separate regression model is estimated for imputation of each variable (i.e., SAPS-PD total score at each time point). Each regression model will include explanatory variables for treatment and all previous (Baseline, Week 2, 3, and 5) values of SAPS-PD total score. After the MAR-based imputations have been generated for SAPS-PD total score at each time point, a value of δ will be added to all imputed values in the SEP-363856 (25, 50 or 75 mg/day) group. This approach assumes that the marginal mean of unobserved subject measurements is worse by δ at each time point after discontinuation compared to the marginal mean of subjects with observed data at the same time point.

No rounding restriction will be applied to imputed continuous values. The imputed SAPS-PD total scores must be within the range of 0 to 45.

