  DDFM=KR SOLUTION COVB;  
  REPEATED AVISITN /SUB=SUBJID TYPE=UN;  
  LSMESTIMATE TRT01PN *AVISITN "SEP-363856 at Week6"  
    [1, 1 4] / E CL;
```

Document: \

Author:

Version Number:
Version Date:

Final 1.0
24FEB2020

Template No: CS_TP_BS016 Revision 4
Effective Date: 01Apr2016

Reference: CS_WI_BS005

LSMESTIMATE TRT01PN *AVISITN "Placebo at Week 6"

[1, 2 4] / E CL;

LSMESTIMATE TRT01PN *AVISITN "SEP-363856 vs Placebo at Week 6"

[1, 1 4] [-1, 2 4] / E CL;

BY _Imputation_;

RUN;

Step 4: Combine results using Rubin's imputation rules:

PROC MIANALYZE parms(classvar=full)=LSMEST;

CLASS TRT01PN *AVISITN;

MODELEFFECTS TRT01PN *AVISITN;

ODS OUTPUT ParameterEstimates=mianLSMEST;

RUN;

Tipping Point Analysis

Step 1: Impute non-monotone missing data using step 1 from above Pattern Mixture Model (PMM) with Placebo-Based MI.

Step 2: Impute the remaining missing data using a MAR-based regression model, and add a value delta to all imputed values in the SEP-3638528 25, 50 or 75 mg/day group:

PROC MI DATA=xxxx_mono seed=12345 NIMPUTE=1 out=xxxx_imp;

VAR TRT01PN <Baseline SAPS-PD total score>;

CLASS TRT01PN ;

MONOTONE REG;

MNAR adjust (SAPS-PD4/delta=xx adjustobs=(TRT01PN ='1')) ;
MNAR adjust (SAPS-PD5/delta=xx adjustobs=(TRT01PN ='1')) ;
MNAR adjust (SAPS-PD6/delta=xx adjustobs=(TRT01PN ='1')) ;
MNAR adjust (SAPS-PD7/delta=xx adjustobs=(TRT01PN ='1')) ;

BY _Imputation_;

RUN;

Step 3: Repeat steps 3 and 4 from above Pattern Mixture Model (PMM) with Placebo-Based MI to analyze the multiply imputed and shifted (by delta) data, and to combine the results using Rubin's imputation rules.

Document:

\

Author:

Version Number:

Final 1.0

Version Date:

24FEB2020

Template No: CS_TP_BS016 Revision 4
Effective Date: 01Apr2016

Reference: CS_WI_BS005

**APPENDIX 4. STEP 4: REPEAT STEP 2 AND 3 ABOVE FOR ALL VALUES OF
DELTA. POTENTIALLY CLINICALLY SIGNIFICANT (PCS) LABORATORY
CRITERIA**

Category	Parameter Name	PCS Low	PCS High
	Age/Gender Restriction, if any		
HEMATOLOGY			
WBC	$\leq 2.8 \times 10^9/L$	$\geq 16 \times 10^9/L$	
Neutrophils (abs)	$< 0.5 \times 10^9/L$	$> 13.5 \times 10^9/L$	
Lymphocytes (abs)	N/A	$> 12 \times 10^9/L$	
Monocytes (abs)	N/A	$> 2.5 \times 10^9/L$	
Eosinophils (abs)	N/A	$> 1.6 \times 10^9/L$	
Basophils (abs)	N/A	$> 1.6 \times 10^9/L$	
Neutrophils (relative)	≤ 0.15	> 0.85	
Lymphocytes (relative)	N/A	≥ 0.75	
Monocytes (relative)	N/A	≥ 0.15	
Eosinophils (relative)	N/A	≥ 0.10	
Basophils (relative)	N/A	≥ 0.10	
Hemoglobin			

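### The placebo-based imputation and tipping-point analyses default to mITT, so a dosed subject with no post-baseline score is dropped instead of imputed

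*SAP*

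**What the plan says.** SAP 5.4 admits to mITT a subject who was randomized, took at least one dose and "had a baseline and at least one post-baseline total score in SAPS-PD or NPI or CGI-S during the DB treatment period". It makes mITT the main efficacy population, and 15.1.3 runs the primary MMRM on it.

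Two sensitivity analyses then relax the MAR assumption. Section 15.1.4.2 imputes missing SEP-363856 values from the placebo model and explains: "This approach does not assume a sustained benefit of experimental treatment after discontinuation". Section 15.1.4.3 adds a penalty delta to imputed SEP-363856 values: "Sensitivity to departures from the MAR assumption will also be investigated using a tipping point analysis". For the former, "Each of the 1000 imputed datasets will be analyzed using the same MMRM model as the primary efficacy analysis"; the latter does the same with its delta-adjusted datasets. Neither section names a population, whereas 15.1.4.5 (complete cases) and 15.1.4.6 (per protocol) name theirs. Section 15.2.4 extends these analyses to CGI-S.

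Pooling follows Rubin's rules. The call in Appendix 3 is "PROC MIANALYZE parms(classvar=full)=LSMEST", with no EDF= option, and the SAP does not state the pooling degrees of freedom. The primary MMRM uses Kenward-Roger.

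**The concern.** Both analyses ask how far the result depends on assumptions about subjects who leave. Restricting them to mITT removes the leavers with the least data, who would carry the most imputed values. A dosed SEP-363856 subject who leaves with no post-baseline score meets neither the placebo-like assumption nor the delta penalty. The imputation models already use baseline SAPS-PD as a predictor, so such a subject can be imputed. The plan in effect does this already for a subject who is in mITT only through an NPI or CGI-S score.

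The other populations tested, complete cases and per protocol, are both subsets of mITT, so no analysis looks at a wider set. At stake is whether a reader can take a surviving sensitivity result as robust to early loss.

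The missing EDF= is a separate and smaller matter. The primary p-value uses a small-sample reference distribution, while the pooled p-values would use an essentially normal one.

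**Working it through.** **1. The plan's own figures.** SAP 3.4 gives "approximately 24 subjects assigned to SEP-363856 and 12 subjects assigned to placebo" and "powers of 59%, 48%, 37%, and 27% to detect treatment effect sizes of 0.8, 0.7, 0.6, and 0.5, respectively", from a "two independent sample t-test method with 2-sided significant level of 0.05". A noncentral t with 34 df and noncentrality d × √(24 × 12/36) = 2.828d gives 59.4%, 48.6%, 37.8% and 28.0%. The stated powers reproduce to within one point, so 24 and 12 are the right denominators below.

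**2. Who can fall out of mITT.**
- Protocol Table 2 schedules the first post-baseline SAPS-PD at Day 8, and the first post-baseline NPI and CGI-S at Day 15. A first-week leaver stays in mITT only through an early-termination (ET) or unscheduled rating.
- Protocol 13.2 asks sites to try to obtain the ET visit, 11.9.9 collects all three scales there, and 11.9.12 collects SAPS-PD and CGI-S at unscheduled visits.
- Against that, SAP 6.9 treats off-period ratings as missing, and 15.1.2 voids a SAPS-PD total if one item is missing.

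The documents give no expected count. I take k = 0 to 3 excluded SEP-363856 subjects as an assumption.

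**3. Placebo-based analysis.** A subject imputed from the placebo model contributes no treatment effect, so adding k such subjects multiplies the mITT effect by (24 − k)/24. The mITT result is overstated by 24/(24 − k):

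| k | (24 − k)/24 | Overstatement | d = 0.8 becomes | Power, all dosed | Power, mITT |
|---|---|---|---|---|---|
| 0 | 1.000 | 0% | 0.80 | 59% | 59% |
| 1 | 0.958 | 4% | 0.77 | 56% | 59% |
| 2 | 0.917 | 9% | 0.73 | 52% | 58% |
| 3 | 0.875 | 14% | 0.70 | 49% | 57% |

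Excluded placebo subjects would be imputed under MAR without penalty, so only exclusions in the SEP-363856 arm matter here.

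**4. Tipping point.** Delta is added only to imputed SEP-363856 values. With j subjects already imputed at Week 6, the estimate shifts by delta × j/(24 − k) in mITT and by delta × (j + k)/24 in all dosed subjects. Section 15.1.4.3 stops at 100% of the LS mean difference. At that cap, assuming j = 3:
- k = 1: 3/23 = 13% of the difference, against 4/24 = 17%.
- k = 2: 3/22 = 14%, against 5/24 = 21%.

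**5. Degrees of freedom.** Without EDF=, Rubin's df is (m − 1)(1 + 1/r)², which equals 999/λ² for m = 1000 and missing-information fraction λ. For an assumed λ of 5% to 30% this is 399,600 down to 11,100, so the critical value is 1.96. With 30 df it is 2.042, and 1.960/2.042 = 0.96: the interval is 4% narrower at the same standard error. Using the Barnard-Rubin small-sample df over the same λ, with complete-data df of 29 or 33 as a stand-in for Kenward-Roger, the range is about 4% to 6%. At t = 2.0, p is 0.0455 with the normal reference and 0.0546 with 30 df.

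**6. Null rejection without EDF=.** Simulations used 24:12 allocation and a Week 6 ANCOVA in place of the MMRM contrast.
- MAR imputation (the tipping analysis at delta = 0) rejected 5.1% to 5.5% over 5% to 20% dropout. Other runs gave 4.7% and 5.0% at 10% and 20% dropout, and up to 6.0% at 0% to 5%, where almost nothing is imputed.
- Placebo-based imputation fell from 4.5% to 1.5% over 5% to 20% dropout. Other runs gave 2.4% at 10% and 0.7% at 20%.

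Monte Carlo error was up to about 0.9 points in the smallest runs.

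**The case against.** The exclusion is narrow. One score on any of three scales keeps a subject in, ET data count and are mapped to the next planned visit (SAP 6.4), and 5.4 does not limit the score to scheduled visits. Protocol 4.3 describes adverse events as seldom leading to discontinuation. There is also a principled reason to keep mITT: 15.1.4.2 sets out to test the robustness of the primary MMRM, and holding the subjects fixed isolates the missing-data assumption. The mITT rule itself comes from protocol 15.2.1. Finally, the Appendix 3 code is schematic, with placeholder dataset names and VAR lists that omit the post-baseline visits, so the absent EDF= may be shorthand.

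Much of this stands. The count may be zero, and then the population change alters nothing. The mITT default is inferred from silence, though it is the natural reading when neighbouring sections name their sets. What the objection does not answer is that no analysis covers dosed subjects outside mITT, and that the plan would not show how many there are.

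A reader might also infer that pooling without EDF= makes both stress tests too lenient. The simulations do not support that: the placebo-based test stayed below 5% throughout, because Rubin's variance is conservative under that imputation.

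**Conclusion.** The point holds, at modest size. Both analyses default to mITT and so omit the leavers with the least data. Each excluded SEP-363856 subject flatters the placebo-based effect: about 4%, 9% or 14% for 1, 2 or 3 of 24. Exclusions also reduce the leverage of delta, for example 13% against 17% of the LS mean difference at the cap. These sizes rest on assumed counts and on treating the excluded subjects as placebo-like. The primary analysis is unaffected.

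It would be tempting to express step 4 as a tipping delta overstated by 28% (k = 1) or 53% (k = 2), the ratios of those shifts. That reads too much into small quantities: the shifts differ by about 4 and 7 percentage points, and if significance survives the 100% cap there is no tipping delta to overstate. What lower leverage does is make it easier to report that no tipping point was found.

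The EDF= omission is a consistency matter. It affects only borderline p-values and the exact delta at which significance is lost.

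**What to change.** 1. In SAP 15.1.4.2 and 15.1.4.3, and in the CGI-S versions under 15.2.4, state that the analysis includes all randomized and dosed subjects with a baseline score on the scale, by randomized arm, with every post-baseline visit imputed for those who have none. The mITT version can be kept beside it for a like-for-like comparison with the primary result.
2. Report by arm the number of dosed subjects excluded from mITT. If it is zero, the two versions coincide.
3. In Appendix 3, add EDF= to PROC MIANALYZE, set to the complete-data Kenward-Roger df for the Week 6 contrast, and state this in the text.

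The cost is a sentence or two in the SAP, one SAS option, one disposition line and a little more analysis work. The downside is slightly less favourable sensitivity results.

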5.7. PER PROTOCOL [PP] POPULATION

The per protocol (PP) population comprises all mITT population subjects who:

- Received assigned study medication as randomized
- Have 14 days or more continuous exposure
- Have 75% - 125% compliance, both limit values inclusive
- Have no major protocol violations, determined by a blinded data review prior to database lock

Selected efficacy endpoints will be analyzed using the PP population. Subjects will be analyzed according to randomized treatment group.

5.8. SAFETY [SAF] POPULATION

The safety population includes all subjects who were randomized and received at least one dose of study drug during the double-blind period. Safety population will be the primary population for the safety analyses. Subjects will be analyzed according to the actual treatment received (i.e., placebo vs SEP-363856).

5.9. OPEN LABEL EXTENSION SAFETY [SAFOL] POPULATION

The OL extension safety population will consist of all subjects who receive at least one dose of study drug during the 12-week open-label extension period. The OL extension safety population will be used for the long-term safety, tolerability, and efficacy analyses. All the by-treatment summaries will be based on the treatment received during the DB period (i.e. SEP-363856 to SEP-363856 vs. Placebo to □ SEP-363856). Changes from baseline in all safety measures will be summarized at each scheduled post-baseline extension visit, based on both the DB baseline and the OL baseline.

6. GENERAL CONSIDERATIONS

6.1. REFERENCE START DATE AND STUDY DAY

Study Day will be calculated from the reference start dates and will be used to show start/ stop day of assessments and events.

Reference start date is defined as the day of the first dose of study medication during double-blind period, (Day 1 is the day of the first dose of study medication), and will appear in every listing where an assessment date or event date appears.

Document:

\

Author:

Version Number:
Version Date:Final 1.0
24FEB2020Template No: CS_TP_BS016 Revision 4
Effective Date: 01Apr2016

Reference: CS_WI_BS005

- If the date of the event is on or after the reference date then:

Study Day = (date of event – reference start date) + 1.

- If the date of the event is prior to the reference date then:

Study Day = (date of event – reference start date).

In the situation where the event date is partial or missing, Study Day, and any corresponding durations will appear missing in the listings. Partial dates will be however presented as is in the listings.

